6.3.5 Use of Antipyretics and Bronchodilators

The use of antipyretics and bronchodilators will be considered study safety endpoints and should be collected with concomitant medications as describe in Protocol Section 6.7.1.

6.4 Concomitant Care and Unscheduled Visits

No study center visits are scheduled other than Screening. Patients will continue to follow with their personal doctors during the study and receive medications at their direction after Screening. The prescription and use of any prohibited medications through Day 14 will be recorded but will not result in the discontinuation of any study procedures. If it determined that the patient is in the need of an unscheduled clinic visit for further evaluation, an unscheduled visit with the personal doctor, or hospitalization, these arrangements will be made. The Investigator will assist in making these arrangements whenever possible. The decision to seek this unscheduled care will be at the discretion of the patient, the personal doctor, or Investigator.

7 ADVERSE EVENTS

7.1 Definitions

7.1.1 Adverse Event

An AE is defined as any untoward medical occurrence associated with the use of a drug in humans, whether or not considered drug related. An AE can therefore be any unfavorable and unintended sign (including an abnormal laboratory finding), symptom, or disease temporally associated with the use of the investigational product whether or not related to the investigational product. An AE can be any sign, symptom, or diagnosis that appears or changes in intensity during the course of the study.

Unchanged chronic conditions are not AEs and should not be recorded on the AE pages of the eCRF. These medical conditions should be adequately documented on the appropriate page of the eCRF (medical history or physical examination). However, medical conditions present on the first day of treatment that worsen in intensity or frequency during the treatment or post-treatment periods in a manner not consistent with natural disease progression should be reported and recorded as AEs. The Investigator will actively solicit this information and assess the event in terms of severity and relationship to the study treatment regimen.

The objective of this study is to assess the effective and safety of NasoVAX in preventing clinical worsening of early COVID-19. The worsening of fever, cough, shortness of breath, resting SpO₂ or resting pulse rate, and symptoms of COVID-19 that are reported in the eDiary during Screening will be captured in aggregate in the eCRF and will not be reported as AEs.

The term AE is used to include any AE whether serious or not serious.

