5.1.2 Stopping Rules

Enrollment and study drug treatment will be temporarily halted pending DMC review for any of the following reasons:

- Any SAE considered possibly or probably related to study drug
 - Any Grade 4 or Grade 5 (death) AE considered possibly or probably related to study drug
 - Three or more patients in the same cohort experience the same Grade 3 AE in the same Medical Dictionary for Regulatory Activities (MedDRA) System Organ Class considered possibly or probably related to study drug
-

Confidential

- Hospitalization rates in either treatment group in individual cohorts exceeding:
 - 15% (Cohort 1 only)
 - 20% (Cohort 2 only)
 - 25% (Cohort 3 only)
- Mechanical ventilation rates in either treatment group in individual cohorts equal to or exceeding:
 - 2 patients (Cohort 1 only)
 - 3 patients (Cohort 2 only)
 - 4 patients (Cohort 3 only)

The DMC will be advised each time a patient dies or is hospitalized. The DMC may unblind individual patients for the assessment of the relationship of the event to study drug. The DMC may recommend resumption of dosing if patient safety is not considered to be at significant risk following analysis.

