7.1.3 Serious Adverse Event

An AE or suspected adverse reaction is considered serious (an SAE) if, in the view of either the Investigator or Sponsor, it results in any of the following outcomes:

- Death
- Life-threatening (An AE is considered life-threatening if, in the view of either the Investigator or Sponsor, its occurrence places the patient or subject at immediate risk of death. It does not include an AE that, had it occurred in a more severe form, might have caused death.)
- Inpatient hospitalization or prolongation of existing hospitalization
- A persistent or significant incapacity or substantial disruption of the ability to conduct normal life functions
- A congenital anomaly/birth defect

Life-threatening means that the patient or subject was at immediate risk of death at the time of the SAE; it does not refer to a serious AE that hypothetically might have caused death if it were more severe. Hospitalization does not include same day surgery, elective surgery, optional admission not associated with a precipitating AE (ie, elective cosmetic surgery), or hospitalization planned before the start of the study for a pre-existing condition that has not worsened. Persistent or significant disability or incapacity means that there is a substantial disruption of a person's ability to carry out normal life functions.

Important medical events that may not result in death, be life-threatening, or require hospitalization may be considered serious when, based upon appropriate medical judgment, they may jeopardize the patient or subject and may require medical or surgical intervention to prevent one of the outcomes listed in this definition. Examples of such medical events include allergic bronchospasm requiring intensive treatment in an emergency room or at home, blood dyscrasias or convulsions that do not result in inpatient hospitalization, or the development of drug dependency or drug abuse.

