7.2 Reporting Responsibilities and Periods

It is the responsibility of the Investigator to perform periodic assessment for AEs. AEs spontaneously reported by the patient or reported in response to an open question from the study personnel (eg, ‘Have you had any health problems since the previous visit/you were last asked?’) or revealed by observation will be recorded.

AEs and concomitant medications will be recorded from the start of study drug administration on Day 1 through 14 or until the time of hospitalization. The AE term, date of AE onset, date of AE resolution (if applicable), severity, causality, action taken for the AE, outcome and whether or not the AE was serious will be recorded.

AEs must be monitored until they are resolved or, stabilized or transferred to the patient’s main healthcare provider for follow up., are clearly determined to be due to a patient’s stable or chronic condition or intercurrent illness(es), the patient is hospitalized or follow-up is no longer possible. Data describing AEs will be recorded in the patient’s medical record and as appropriate, an SAE report form. SAEs will be reported to the Sponsor as described in Protocol Section 9.6.

Any SAE that the Investigator considers to be related to study drug and occurs at any time after completion of the study must be reported to the Sponsor or designee. If at the time the Investigator initially reports an SAE, the event has not resolved, the Investigator must provide a follow-up report as soon as it resolves (or upon receipt of significant information if the event is still ongoing).

Note that for the purposes of this study, hospitalization due to worsening fever, cough or shortness of breath, resting SpO₂ or resting pulse rate or symptoms of COVID-19 that are reported at Baseline will not be considered an SAE.

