7.6 Procedures for Recording and Reporting Adverse Events

7.6.1 *Recording Adverse Events*

To improve the quality and precision of AE data, Investigators should observe the following guidelines:

- Whenever possible, use recognized medical terms when recording AEs on the AE page of the eCRF. Do not use colloquialisms, jargon, or abbreviations.
 - If known, record the diagnosis (ie, disease or syndrome) rather than component signs and symptoms on AE pages of the eCRF (eg, record “congestive heart failure” rather than “dyspnea”, “rales”, and “cyanosis”). However, signs and symptoms that are considered unrelated to an encountered syndrome or disease should be recorded as individual AEs on the eCRF page. For example, if congestive heart failure and severe headache are observed at the same time, each event should be recorded as an individual AE.
 - Adverse events occurring secondary to other events (ie, sequelae) should be identified by the primary cause. A primary AE, if clearly identifiable, generally represents the most accurate clinical term to record on the AE page of the eCRF. If a primary SAE is recorded on an AE eCRF page, events occurring secondary to the primary event should be described in the narrative description of the event.
 - Any laboratory abnormalities that are identified by the Investigator as clinically significant, as applicable, are to be considered AEs and recorded on the AE eCRF page.
-

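### The AE/SAE exemption for COVID-19-like worsening has no relatedness condition and conflicts with other rules in the plan, so drug-caused worsening may go ungraded, unrated and uncounted

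*SAP*

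**What the plan says.** **The exemption.** SAP 7.1.1 lists worsening fever, cough, shortness of breath, resting SpO2 or pulse rate, and "symptoms of COVID-19 that are reported in the eDiary during Screening". It says that these "will be captured in aggregate in the eCRF and will not be reported as AEs". Protocol 9.1.1 has the same rule.

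**Its extension to SAEs.** SAP 7.2 covers "hospitalization due to worsening fever, cough or shortness of breath, resting SpO₂ or resting pulse rate" and ends with "symptoms of COVID-19 that are reported at Baseline will not be considered an SAE". SAP 7.6.2 repeats this for hospitalizations and adds deaths, as does SAP 6.2.6 for deaths. The matching protocol sections are 9.2, 9.6.3 and 8.2.6.

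**The competing rules.**
- Just before the exemption, SAP 7.1.1 says that conditions present on the first day of treatment that worsen "in a manner not consistent with natural disease progression should be reported and recorded as AEs".
- SAP 9.10.1 counts as treatment-emergent an AE that was present when treatment began and then worsened.
- SAP 9.10.2 keeps a symptom change out of the AE log unless it meets SAE criteria. It also leaves out of the AE count any logged event that the eDiary captures too.

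**What depends on AE or SAE status.** Incidence and severity of AEs is the first safety endpoint in SAP 3.3. Three halting rules in SAP 5.1.2 count only events rated possibly or probably related. The first is "Any SAE considered possibly or probably related to study drug"; the others are a related Grade 4 or 5 AE, and the same related Grade 3 AE in three or more patients of a cohort.

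**The concern.** The exemption is worded by sign, and no sentence in it asks about relatedness to study drug. A febrile or respiratory reaction to a vector given into the nose could show as the listed signs. If a site applies the exemption as written, such a reaction is not an AE. It then gets no CTCAE grade and no causality rating, and cannot count toward the three related-event halting rules.

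Another site could apply the natural-progression sentence to the same patient and record an AE. The plan does not say which rule prevails, so AE counts would depend partly on each site's reading. If the exemption were the usual reading, NasoVAX could look better tolerated in the AE tables than it was.

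**Working it through.** The plan gives no figure on this point to reproduce. The check is first a comparison of texts, then a sizing under stated assumptions.

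**1. How the rules treat one case: worsening that the investigator attributes to study drug**

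| Rule | Result |
|---|---|
| SAP 7.1.1, exemption | Not an AE |
| SAP 7.1.1, natural-progression sentence | An AE, if the condition was present on the first day and the course is not natural progression |
| SAP 9.10.1, TEAE definition | Worsening of an AE present at treatment start is treatment-emergent |
| SAP 9.10.2, SAE exception | An AE only if SAE criteria are met |
| SAP 7.2 and 7.6.2 | Hospitalization or death from it is not an SAE |
| SAP 9.10.2, de-duplication | Not counted if the eDiary also captured it, even when logged as an AE |

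The second to fourth rows conflict with the first. The fourth and fifth rows also conflict: the exception keeps events that meet SAE criteria, and 7.2 says that hospitalization for these signs does not meet them.

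**2. Does the Screening clause confine the exemption?** It is unclear whether the clause limits every listed sign or only the symptoms named last. Even on the narrow reading, Protocol 5.2 (criterion 3) requires at least one of fever, cough or shortness of breath at entry. Every patient therefore has at least one exempt sign.

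**3. Hospitalized reactions.** If a drug-related hospitalization were an SAE, one event would meet the related-SAE rule. If it is exempt, the automatic triggers left are the hospitalization-rate rule and, where it applies, the ventilation rule. Inputs are the NasoVAX arm sizes of 10, 14 and 24 (SAP 4.1) and the rates to be exceeded of 15%, 20% and 25% (SAP 5.1.2). The smallest k with k/n above the limit is:
- Cohort 1: 2/10 = 20.0% (1/10 = 10.0% is not enough)
- Cohort 2: 3/14 = 21.4% (2/14 = 14.3% is not enough)
- Cohort 3: 7/24 = 29.2% (6/24 = 25.0% equals the limit and does not exceed it)

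Assume drug-caused hospitalization rates p of 2%, 5% and 10%. These rates are not in the documents. Background admissions are ignored. P(at least one) = 1 − (1 − p)^n, and P(rate rule met) = P(X ≥ k) with X binomial(n, p).

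| Cohort | At least one event, p = 2 / 5 / 10% | Rate rule met, p = 2 / 5 / 10% |
|---|---|---|
| 1 (n = 10, k = 2) | 18 / 40 / 65% | 1.6 / 8.6 / 26.4% |
| 2 (n = 14, k = 3) | 25 / 51 / 77% | 0.2 / 3.0 / 15.8% |
| 3 (n = 24, k = 7) | 38 / 71 / 92% | <0.1 / <0.1 / 0.7% |

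Example for Cohort 3 at 5%: 1 − 0.95^24 = 0.708, while P(X ≥ 7) is about 0.0001.

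**4. Grade 3 reactions managed at home.** Assume that 10% to 15% of the 24 NasoVAX patients in Cohort 3 have one, again with no source in the documents. If all were the same event, P(X ≥ 3) would be 0.436 to 0.720. The rule needs the same Grade 3 AE, so pooling event types overstates this. Split evenly into two types, treated as independent, each has P(X ≥ 3) = 0.116 at 5% or 0.267 at 7.5%. The chance that either reaches three is 1 − (1 − 0.116)² = 22%, up to 1 − (1 − 0.267)² = 46%. Events left unrecorded under the exemption add nothing to this count.

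**The case against.** A reader might infer that drug-caused fever, respiratory, SpO2 or pulse reactions are never AEs, or are missing from the safety results. The documents do not support that.

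- The natural-progression sentence and the SAE exception in SAP 9.10.2 both point the other way. The defect is an unresolved conflict, not a settled exclusion.
- The signs are reported by arm. SAP 9.10 summarizes oral temperature and use of antipyretics and bronchodilators. SAP 9.10.2 tabulates symptoms by maximum severity, SAP 9.10.3 summarizes vital signs, and SAP 9.9.2 to 9.9.4 analyze SpO2 and pulse rate. A sizeable drug effect could show as a difference between randomized groups.
- The DMC is told of every hospitalization and death, receives the exempt narratives in real time, may unblind to judge relationship to study drug, and reviews safety before each new cohort. The hospitalization and ventilation halting rules do not depend on AE status.
- SAP 6.2.6 does report deaths from causes other than COVID-19 as SAEs.
- SAP 7.3.2 reserves a rating of possibly related for events unlikely to be due to concurrent disease. All patients have COVID-19, so few such signs might be rated related even without the exemption.

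All of this stands and limits the consequence. It does not remove it. The summaries by arm carry no causality rating and feed no related-event halting rule. The specific DMC narrative route covers hospitalizations and deaths, so a reaction managed at home has no defined route to a causality rating.

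Two further inferences also fail. SAP 7.1.3 gives "allergic bronchospasm requiring intensive treatment in an emergency room or at home" as an example of an important medical event, but bronchospasm is not an exempt sign, and SAP 7.6.1 asks for the diagnosis rather than its component signs. SAP 7.6.1 also says "Adverse events occurring secondary to other events (ie, sequelae) should be identified by the primary cause", but that is a recording guideline. It does not say that complications of COVID-19 go unrecorded.

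**Conclusion.** The point holds as a conflict that needs reconciling. The exemption and its SAE extensions contain no relatedness condition, and they contradict other rules on what is recorded and counted. Drug-caused worsening may therefore be left out of the AE, SAE and TEAE tables, lack a grade and causality rating there, and not reach the three related-event halting rules. The loss is confined to those tables, ratings and rules.

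The firm part of the size is the change of automatic trigger, from one related SAE to 2, 3 or 7 hospitalizations in an arm. It assumes full arms as denominators. On a running denominator, which the plan neither adopts nor rules out, one early admission could exceed the limit. It also assumes that each drug-caused admission would have been rated related. Background admissions would bring the rate rule closer. The probabilities only illustrate assumed event rates; the documents support no particular rate. The conclusion rests on the text and does not depend on them.

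**What to change.** Reconcile SAP 6.2.6, 7.1.1, 7.2, 7.6.2, 9.10.1 and 9.10.2 with Protocol 8.2.6, 9.1.1, 9.2 and 9.6.3, as follows:

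1. Limit the exemption, including its extension to hospitalization and death, to worsening that the investigator judges consistent with the natural course of COVID-19 and not related to study drug.
2. State that worsening of any listed sign judged possibly or probably related, or not consistent with natural progression, is recorded, graded and rated as an AE, or as an SAE if it meets SAP 7.1.3.
3. In SAP 9.10.2, align the SAE exception with this rule and state that de-duplication against the eDiary does not remove such an event. Without this step, a logged drug-related cough or dyspnea would still leave the counts.
4. In SAP 9.10.1, confirm that these events count as TEAEs.
5. Use one reference point for pre-existing symptoms and say whether it limits all the listed signs or only the symptoms. SAP 7.1.1 refers to the eDiary during Screening, SAP 7.2 to Baseline and Protocol 9.2 to the time before treatment.

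The halting thresholds stay as they are. Ordinary COVID-19 progression remains outside the AE log, so the purpose of the exemption is kept. The cost is a wording change in both documents, a few more AE records with a causality rating, and slightly less favourable AE counts. No visit or procedure is added.

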7.1.2 Unexpected Adverse Drug Experience

An unexpected adverse drug experience is defined as an adverse experience, the nature or severity of which is not consistent with the reference safety information in the Investigator's Brochure.

For the purpose of expedited reporting of IND-Safety Reports, only unexpected SAEs considered possibly or probably related to study medication by the Sponsor and unexpected SAEs (see SAEs Protocol Section 9.1.3) will be considered IND-Safety Reports.

7.1.3 Serious Adverse Event

An AE or suspected adverse reaction is considered serious (an SAE) if, in the view of either the Investigator or Sponsor, it results in any of the following outcomes:

- Death
- Life-threatening (An AE is considered life-threatening if, in the view of either the Investigator or Sponsor, its occurrence places the patient or subject at immediate risk of death. It does not include an AE that, had it occurred in a more severe form, might have caused death.)
- Inpatient hospitalization or prolongation of existing hospitalization
- A persistent or significant incapacity or substantial disruption of the ability to conduct normal life functions
- A congenital anomaly/birth defect

Life-threatening means that the patient or subject was at immediate risk of death at the time of the SAE; it does not refer to a serious AE that hypothetically might have caused death if it were more severe. Hospitalization does not include same day surgery, elective surgery, optional admission not associated with a precipitating AE (ie, elective cosmetic surgery), or hospitalization planned before the start of the study for a pre-existing condition that has not worsened. Persistent or significant disability or incapacity means that there is a substantial disruption of a person's ability to carry out normal life functions.

Important medical events that may not result in death, be life-threatening, or require hospitalization may be considered serious when, based upon appropriate medical judgment, they may jeopardize the patient or subject and may require medical or surgical intervention to prevent one of the outcomes listed in this definition. Examples of such medical events include allergic bronchospasm requiring intensive treatment in an emergency room or at home, blood dyscrasias or convulsions that do not result in inpatient hospitalization, or the development of drug dependency or drug abuse.

7.2 Reporting Responsibilities and Periods

It is the responsibility of the Investigator to perform periodic assessment for AEs. AEs spontaneously reported by the patient or reported in response to an open question from the study personnel (eg, ‘Have you had any health problems since the previous visit/you were last asked?’) or revealed by observation will be recorded.

AEs and concomitant medications will be recorded from the start of study drug administration on Day 1 through 14 or until the time of hospitalization. The AE term, date of AE onset, date of AE resolution (if applicable), severity, causality, action taken for the AE, outcome and whether or not the AE was serious will be recorded.

AEs must be monitored until they are resolved or, stabilized or transferred to the patient’s main healthcare provider for follow up., are clearly determined to be due to a patient’s stable or chronic condition or intercurrent illness(es), the patient is hospitalized or follow-up is no longer possible. Data describing AEs will be recorded in the patient’s medical record and as appropriate, an SAE report form. SAEs will be reported to the Sponsor as described in Protocol Section 9.6.

Any SAE that the Investigator considers to be related to study drug and occurs at any time after completion of the study must be reported to the Sponsor or designee. If at the time the Investigator initially reports an SAE, the event has not resolved, the Investigator must provide a follow-up report as soon as it resolves (or upon receipt of significant information if the event is still ongoing).

Note that for the purposes of this study, hospitalization due to worsening fever, cough or shortness of breath, resting SpO₂ or resting pulse rate or symptoms of COVID-19 that are reported at Baseline will not be considered an SAE.

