### **6.7.1 Prohibited Prior and Concomitant Medications**

Prohibited prior and concomitant medications are as follows:

- Hydroxychloroquine within 4 months or chloroquine within 9 months of Screening
- Any treatment known to affect the immune system, including but not limited to oral or intravenous corticosteroids, alkylating drugs, antimetabolites, cytotoxic drugs, radiation, immune-modulating biologics, within 30 days of Screening
- Live vaccines (such as live influenza vaccinations or live travel vaccinations) within 30 days of Screening and through Day 14 post study drug administration
- Receipt of any investigational drug or treatment within 30 days of Screening.

The above medications are prohibited through Day 14 or hospitalization, and all other concomitant medications are permitted. If a patient is hospitalized due to COVID-19, there are no restrictions regarding concomitant medications. However, all medications administered, including antipyretics, bronchodilators, and supplemental oxygen requirements, are to be documented in the eCRF.

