3.3 Safety Endpoints

Safety endpoints are:

- Incidence and severity of adverse events (AEs)
- Oral temperatures
- Use of antipyretics and bronchodilators
- Hospital length of stay, and intensive care unit (ICU) length of stay

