4.7 Prior and Concomitant Therapy

In the interests of patient safety and acceptable standards of medical care, both the Investigator and patient personal physician(s) will be permitted to prescribe additional treatment(s) at his/her discretion.

Any medications that are ongoing at Screening are to be documented in the electronic case report form (eCRF). Thereafter, all concomitant medications, including supplemental oxygen, through 30 days after study drug administration are to be documented in the eCRF.

Concomitant medications, including supplemental oxygen, are to be recorded in the source documents and in the eCRF.

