6.2.5 Additional Data Collection in Hospitalized Patients

Additional data to be collected for patients hospitalized due to COVID-19 through Day 42 to include the following:

- Date and time of hospital admission and discharge
- If transferred to ICU, date and time of ICU admission and discharge
- Requirement for oxygen (yes/no), and if yes, method of oxygenation (mask/nasal prongs, non-invasive ventilation, or high-flow oxygen; intubation and mechanical ventilation
 - If required ventilation, start date and time of ventilation, method of ventilation including whether intubated (yes/no)
- Change in ambulatory status
- Death

It is anticipated that most of this information will be obtained from the medical record. When necessary, a family member, designated legal representative or caregiver, as permitted by informed consent, will be contacted if the patient has expired or is too ill or otherwise unable to provide this information.

The rate (liters/min) of oxygen administered is to be captured as a concomitant medication. If, in the Investigator's opinion, a patient required a higher level of oxygenation, but did not receive due to resource availability, this should be documented.

Furthermore, if, in the Investigator's opinion, the patient required a higher level of care (ie, admittance to the ICU) but did not receive due to resource availability, this should be documented.

6.2.6 *Vital Status*

Vital status is to be documented at each study contact. If the patient died due to a reason other than COVID-19, the primary cause of death is to be recorded and reported as an SAE. Death due to worsening fever, cough, shortness of breath, resting SpO₂ or resting pulse rate or COVID-19 symptoms that are reported at Screening (Protocol Section 8.1.2) is not considered to be an SAE in the context of this study although cause of death will be reviewed by the DMC in real time.

6.3 **Safety Assessments**

6.3.1 *Height, Weight and Body Mass Index (BMI)*

Height (cm) and weight (kg) will be measured and recorded at Screening. BMI will be subsequently be calculated from these measurements.

6.3.2 *Physical Examination*

A cardiovascular and respiratory-focused physical examination will be performed by trained medical personnel during Screening.

6.3.3 *Screening Vital Signs*

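### Two incompatible recording windows for concomitant medications leave in-hospital antipyretic and bronchodilator use, a named safety endpoint, open to loss at hospitalization

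*SAP*

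**What the plan says.** Antipyretic and bronchodilator use is a safety endpoint in both documents (Protocol 3.3; SAP 3.3: "Use of antipyretics and bronchodilators"). Its data come from the concomitant-medication records, for which the documents give two rules.

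- **Shorter rule.** SAP 7.2, and Protocol 9.2 in the same words: "concomitant medications will be recorded from the start of study drug administration on Day 1 through 14 or until the time of hospitalization".
- **Longer rule.** SAP 4.7, and Protocol 6.7 in the same words: "all concomitant medications, including supplemental oxygen, through 30 days after study drug administration are to be documented in the eCRF".

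Several other places fit only a rule that continues beyond Day 14 or admission:

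- Protocol 6.7.1 (repeated in SAP 4.7.1) says "If a patient is hospitalized due to COVID-19, there are no restrictions regarding concomitant medications". The next sentence is "However, all medications administered, including antipyretics, bronchodilators, and supplemental oxygen requirements, are to be documented in the eCRF".
- The Schedule of Events (Protocol Table 1; SAP Table 2) marks concomitant medications at the Day 21 and Day 28 contacts.
- Protocol 8.2.5 and SAP 6.2.5, which cover hospitalized patients through Day 42, say "The rate (liters/min) of oxygen administered is to be captured as a concomitant medication".

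For the endpoint itself, SAP 6.3.5 says these medications "should be collected with concomitant medications as describe in Protocol Section 6.7.1"; Protocol 8.3.5 makes the same referral. SAP 9.10 summarizes the endpoint descriptively. It states neither a time window nor how use in hospitalized patients is counted.

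**The concern.** The shorter rule ends recording at admission, and hospitalization is a component of the primary endpoint. If a site applies it, how long a patient's medication use is observed depends on that patient's outcome. The arm with more admissions would lose more use. If admitted patients start these drugs in hospital, a real difference between arms in antipyretic or bronchodilator use would shrink. Protocol 5.1 allows up to 12 centers, so different sites could also follow different sections. The pooled table would then mix two definitions of the same endpoint, with nothing in SAP 9.10 to separate them.

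**Working it through.** The plan states no figure for this endpoint, so there is nothing to reproduce. The check compares the text and then bounds the possible loss.

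**1. Recording windows compared**

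| Source | End of recording | In-hospital use recorded? |
|---|---|---|
| Protocol 9.2, SAP 7.2 | Day 14 or admission | No |
| Protocol 6.7, SAP 4.7 | 30 days after dosing | Not excluded |
| Protocol 6.7.1, SAP 4.7.1 | None stated | Yes, both drug classes named |
| Schedule of Events | Day 28 contact (±2 days) | Not addressed |
| Protocol 8.2.5, SAP 6.2.5 | Day 42 | Yes, oxygen rate |

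The first row cannot be reconciled with the others. SAP 9.13 lets the SAP override the protocol, but the SAP holds both rules, so that clause does not settle it.

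**2. Length of the windows.** SAP 9.1 makes the dosing day Day 1, so 30 days after dosing is study Day 31. A patient never admitted has 14 recorded study days under the shorter rule and 31 under the longer. A patient admitted on Day *d*, up to Day 14, has about *d* days under the shorter rule and no in-hospital use. The last scheduled contact, Day 28 ±2, falls on Day 30 at the latest, so the 30-day window also outlasts the scheduled calls. The Appendix B script for Days 21 and 28 has no medication question.

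**3. How many patients could be affected.** Inputs are the planned arm sizes (10, 14 and 24; SAP Table 1) and the hospitalization thresholds that must not be exceeded (15%, 20% and 25%; Protocol 7.2, SAP 5.1.2).

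- Cohort 1: 1/10 = 10.0% is allowed; 2/10 = 20.0% exceeds 15%.
- Cohort 2: 2/14 = 14.3% is allowed; 3/14 = 21.4% exceeds 20%.
- Cohort 3: 6/24 = 25.0% is allowed; 7/24 = 29.2% exceeds 25%.
- Total: (1 + 2 + 6)/48 = 9/48 = 18.75% of an arm.

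**4. Understatement of any-use in one arm.** Let *h* be the proportion admitted, *a* the probability of use at home before admission, and *b* the probability of use in hospital. Assume *a* and *b* are independent and every site follows the shorter rule. Then

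loss = *h* × (1 − *a*) × *b*.

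The documents give neither *a* nor *b*, so the values below are assumptions, with *h* = 18.75%:

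| *a* | *b* | Loss (percentage points) |
|---|---|---|
| 0% | 100% | 18.75 × 1.00 × 1.00 = 18.75 |
| 10% | 60% | 18.75 × 0.90 × 0.60 = 10.1 |
| 50% | 60% | 18.75 × 0.50 × 0.60 = 5.6 |
| 80% | 60% | 18.75 × 0.20 × 0.60 = 2.25 |

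The lower bound is 0, when every admitted patient has already used the drug at home or none uses it in hospital.

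**5. Difference between arms.** With the same *a* and *b* in both arms, the lost difference is the gap in admission rates × (1 − *a*) × *b*. For an assumed 10-point gap and *b* = 60%, this is 5.4 points at *a* = 10%, 3.0 at 50% and 1.2 at 80%. The largest of these is about 0.054 × 48 = 2.6 patients.

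**The case against.** The strongest reply is that the endpoint has its own collection rule. Protocol 8.3.5 and SAP 6.3.5 send it to Protocol 6.7.1, which names both drug classes directly after the sentence on hospitalized patients. The schedule and the Day 42 oxygen instruction point the same way. The contrary text is a mention of medications inside an adverse-event reporting section; Protocol 8.3.4 and SAP 6.3.4 give the same Day 14/hospitalization period for adverse events alone. A careful site would probably keep recording.

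This stands as an argument about the likely intent, and it lowers the chance of loss. It does not remove the conflict: Protocol 6.7.1 gives no end date, nothing says that it overrides 9.2, and SAP 9.10 does not say which records count.

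The reply also limits the consequence. The endpoint is descriptive, and admissions are captured separately in the primary endpoint, a secondary endpoint and length of stay. Where home use is common, as it may be for antipyretics, little any-use is lost. All of this stands.

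A reader might infer that in-hospital drugs and oxygen rates will simply be missing. The documents do not support that, because a site would have to set aside 6.7, 6.7.1, 8.2.5, 8.3.5 and the schedule. A reader might also infer that recording is cut off in everyone who worsens. The cut at admission touches only those hospitalized; a patient who worsens by SpO2 alone is cut at Day 14 like anyone else.

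**Conclusion.** The contradiction is real, appears in both documents, and is not resolved by any precedence rule in them. The consequence is conditional: if sites follow Protocol 9.2/SAP 7.2, in-hospital use is lost, the safety endpoint is truncated by outcome, and a difference between arms could be understated.

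The understatement of any-use from the hospitalization cut ranges from 0 to 18.75 points per arm. The top needs 9 of 48 admitted, every admitted patient's first use to be in hospital, and every site to apply the shorter rule. The 9/48 is a reference point and not a ceiling, because exceeding a threshold leads to a temporary halt and DMC review, after which dosing may resume. The range leaves out use that begins after Day 14 in patients never admitted, which the shorter rule would also miss.

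A reader might infer that the efficacy conclusion is at risk. It is not: the primary test uses SpO2 and hospitalization, neither of which depends on medication records. The point should be corrected, but it does not threaten the trial's main result.

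**What to change.** 1. In Protocol 9.2 and SAP 7.2, delete the reference to concomitant medications from the Day 14/hospitalization sentence. The adverse-event period is unchanged, and the Protocol 6.7/SAP 4.7 window then governs in and out of hospital.
2. Keep the collection of in-hospital oxygen data through Day 42 in Protocol 8.2.5 and SAP 6.2.5. Ending all medication recording at Day 28 would create a new conflict with those sections.
3. For patients who are not hospitalized, align the 30-day end date in Protocol 6.7/SAP 4.7 with the last scheduled contact, and add a medication question to the Appendix B script.
4. In SAP 9.10, tabulate antipyretic and bronchodilator use over one stated window, common to all Safety Analysis Set patients, that does not end at hospitalization. In choosing its length, note that a Day 14 window rests on daily calls but leaves out most hospital use after a late admission.

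The cost is minor wording in Protocol 6.7, 9.2 and Appendix B and in SAP 4.7, 7.2 and 9.10. The protocol changes need an amendment and IRB approval (Protocol 12.5). Medication data must be abstracted from the records of admitted patients, which Protocol 6.7.1 already requires.
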